1.1. Synopsis

Protocol Title: A Study to Investigate Local Infusion Site Pain after Infusion of Excipients across Infusion Sites and Infusion Depths

Short Title: Investigation of Infusion Site Pain after Infusion of Excipients across Infusion Sites and Infusion Depths

Rationale:

Local infusion site pain may vary between anatomical sites of infusion and between depths of infusion. This study will assess the contribution of infusion site and depth, as well as excipients such as sodium citrate and treprostinil, on local infusion site pain in patients with type 1 diabetes mellitus (T1D) on continuous subcutaneous insulin infusion (CSII).

Objectives and Endpoints

Objectives	Endpoints
Part A	
Primary	
To investigate local infusion site pain for infusions of sodium citrate and treprostinil in Humalog diluent with magnesium chloride (without insulin) in the abdominal, arm, thigh, and buttock areas in participants with T1D on CSII.	VAS pain score
Secondary	
To investigate local infusion site pain of 2 different cannula insertion depths (6 mm and 9 mm) in participants with T1D on CSII	VAS pain score

The image consists of a large, bold, red text 'CCI' centered on a solid black rectangular background. The font is a sans-serif style.

Abbreviations: CSII = continuous subcutaneous insulin infusion; VAS = visual analog scale; T1D = type 1 diabetes mellitus.

Overall Design

Study I8B-MC-ITTC is a 1-/2-center, participant-(Part A CCI [REDACTED]) and investigator- CCI [REDACTED] blind, 2-part randomized crossover study in adults (18 to 69 years of age, inclusive) with T1D on CSII.

Part A of this study will be a 1-/2-center, randomized, 1 day 5-period crossover based on the order of infusion sites and depths, blinded (between infusion depths), open-label single-treatment study conducted in participants with T1D.

CCI
[REDACTED]

Number of Participants:

Approximately 46 participants will be randomly assigned to study intervention such that approximately 40 evaluable participants complete Part A CCI [REDACTED] of the study. CCI [REDACTED]

Intervention Groups and Duration:

Interventions groups

Part A

- Following an informed consent and a screening visit, participants will come to the clinical research unit (CRU) the evening prior to Day 1 for Part A. Participants will continue use of their personal pump to administer insulin at the currently employed infusion site and infusion settings. Participants will be instructed to avoid the use of the central abdominal area for their personal infusion set (for at least 3 days) prior to arrival at the CRU. Thickness of the subcutaneous (SC) fat layer at the abdominal, arm, thigh, and buttock areas will be assessed by ultrasound.
- Each Medtronic™ MiniMed™ 770G pump reservoir will be filled with study treatment (sodium citrate and treprostinil in Humalog diluent with magnesium chloride [without insulin]) by a qualified site staff member, a MiniMed™ Mio™ Advance infusion set will be attached to the reservoir, the reservoir loaded into the pump, and the infusion set tubing primed until drops are seen at the tip. Six mm cannula will be inserted into each of these areas (abdomen [at least 5 cm away from the umbilicus in the left or right lower quadrants], posterior aspect of the upper arm, anterior or lateral thigh, and upper buttock), avoiding areas of lipohypertrophy and surgical scars. At the abdominal area only, a 9 mm cannula will also be inserted into the opposite side of the lower abdomen. The infusion set cannula will be filled with 0.6 unit for both 6 mm and 9 mm cannula (while no insulin will be infused by the study pumps, for simplicity, volumes and rates will be described in units and units/hour where 1 unit = 10 μ L).
- Participants will be randomly assigned to a treatment sequence to indicate the order of the infusion sites being evaluated.

- The first infusion site will be initiated according to the treatment sequence and a basal infusion rate of 1 U/h will be started. The same procedure will occur at the subsequent infusion sites according to the treatment sequence with an approximate 30-minute interval between initiation of the previous infusion site.
- Approximately 3 hours after start of the basal infusion rate, a bolus dose of 15 U given at quick speed (15 U/min) will be delivered to each infusion site according to the treatment sequence with an approximate 30-minute interval between infusion sites.
- A second bolus dose of 15 U given at quick speed (15 U/min) will be delivered approximately 6 hours after the start of the basal infusion to each infusion site according to the treatment sequence with an approximate 30-minute interval between infusion sites.
- A third bolus dose of 15 U given at quick speed (15 U/min) will be delivered approximately 9 hours after the start of the basal infusion to each infusion site according to the treatment sequence with an approximate 30-minute interval between infusion sites.
- Participants will rate the pain at each infusion site with each bolus dose at the following approximate time points: 5 minutes before the administration of a bolus dose and 1 and 15 minutes after the start of each bolus dose. Study infusion sets and pumps will be removed, the infusion sites will be evaluated for acute infusion reactions, and the participant will be discharged.

The image consists of a large, bold, red text "CCI" centered on a solid black rectangular background. The text is in a sans-serif font and is approximately three times as tall as it is wide.

[figure not shown]
Duration

The approximate duration of study participation for each participant may be up to 36 days, across the following study intervals:

- Screening, approximately 28 days
- Treatment period, 2 visits over 5 days (1 day for Part A CCI [REDACTED]
[REDACTED])
- Follow-up period CCI [REDACTED]

Data Monitoring Committee: No

1.2. Schema

1.3. Schedule of Activities (SoA)

Table 1 Trial Flow Chart

Trial Period	Screening Period		Study Period	Follow-up-Televisit/early discontinuation	Comments
Visit no.	0	1	2 (Part A) CCI	4	
Timing	≥1 day before Visit 1	≤28 days prior to Visit 2	at least 3 days between Visit 2 and Visit 3	CCI	
In-house Visit/Period			see Table 2	CCI	
Informed consent	X	X			At Visit 1, check that informed consent has been signed and dated
Fasting		X			
Inclusion/exclusion criteria		X			At Visit 2, confirm participant compliance
Demographic data		X			
Smoking and alcohol consumption habits		X			
Medical history/Pre-existing Conditions		X			
Weight		X	X		
Height		X			
Alcohol breath test/urine drug screen		X	X		
Physical examination		X			
Vital signs		X	X		
12-lead ECG		X			
Haematology		X			
Biochemistry		X			
Coagulation		X			
Urinalysis		X			
Infectious serology		X			

Trial Period	Screening Period		Study Period	Follow-up- Televisit/early discontinuation	Comments
Visit no.	0	1	2 (Part A) CCI	4	
Timing	≥1 day before Visit 1	≤28 days prior to Visit 2	at least 3 days between Visit 2 and Visit 3	CCI	
In-house Visit/Period			see Table 2	CCI	
Pregnancy test		X	X		Only required for women of childbearing potential Serum at the screening visit and urine at Visits 2 and 3
FSH		X			This is only for women with both more than 12 months of amenorrhea and age of ≤55 (see Sections 10.2 and 10.4)
HbA1c		X			
Ultrasound			X		Thickness of the subcutaneous (SC) fat layer will be assessed at the abdominal areas (lower right and left), arm, thigh, and buttock.
Local Infusion site pain (VAS)			X		See Table 2 and Table 3 for collection times
Local Infusion site reactions			X		After removal of each infusion set
CCI Platform			X		Collect image of each local infusion site prior to insertion and after removal of each infusion set
AEs/Product Complaints		X	X	X	
Concomitant Medications		X	X	X	

Trial Period	Screening Period		Study Period		Follow-up- Televisit/early discontinuation	Comments
Visit no.	0	1	2 (Part A) CCI		4	
Timing	≥ 1 day before Visit 1	≤ 28 days prior to Visit 2	at least 3 days between Visit 2 and Visit 3		CCI	
In-house Visit/Period			see Table 2	CCI		
Meals (breakfast, lunch, and dinner)			X			Breakfast will be provided prior to study activities. Lunch will be provided after completion of the first bolus assessments. Dinner will be provided after completion of the second bolus assessments

Abbreviations: AE = adverse event; BMI = body mass index; ECG = electrocardiogram; HbA1c = hemoglobin A1c; no. = number; VAS = visual analog scale.

Table 2 Assessment Schedule for Visit 2 (Part A)

Approx. hour	Nominal timing	Activity	Other
Day -1		Participant arrives after dinner for overnight stay at the trial site and continued eligibility will be checked. The participant will continue personal diabetes management care. Participants will be instructed to avoid the use of the central abdominal area for their personal infusion set (for at least 3 days) prior to arrival at the CRU and continue insulin infusion with their personal insulin pump.	SARS-CoV-2 test may be performed according to the site general procedures AEs, concomitant medication, alcohol breath test, vital signs, urine pregnancy test
Day 1		Breakfast	
		Measure and record adipose thickness by ultrasound at infusion sites Collect image of each local infusion site prior to insertion of the corresponding infusion set using CCI Platform	These measurements may be performed at any time after the subject's arrival on Day -1 until infusion set insertion. Each local infusion site should be labeled and have a unique identifier for CCI Platform image acquisition
		Study pumps loaded with study treatment	
+0 h		Insert infusion set cannula into infusion site 1 and start pump at a basal rate of 1 U/h	
+0.5 h (± 5 min)		Insert infusion set into infusion site 2 and start pump at a basal rate of 1 U/h	
+1 h (± 5 min)		Insert infusion set into infusion site 3 and start pump at a basal rate of 1 U/h	
+1.5 h (± 5 min)		Insert infusion set into infusion site 4 and start pump at a basal rate of 1 U/h	
+2.0 h (± 5 min)		Insert infusion set into infusion site 5 and start pump at a basal rate of 1 U/h	
+3.0 h (± 3 min)	-5 min ^b	Collect VAS score for infusion site 1	
	0 min	Administer 15 U bolus to infusion site 1 at quick bolus speed (15 U/min)	
	+1 min ^a	Collect VAS score for infusion site 1	
	+15 min ^b	Collect VAS score for infusion site 1	
+3.5 h (± 3 min)	-5 min ^b	Collect VAS score for infusion site 2	

Approx. hour	Nominal timing	Activity	Other
	0 min	Administer 15 U bolus to infusion site 2 at quick bolus speed (15 U/min)	
	+1 min ^a	Collect VAS score for infusion site 2	
	+15 min ^b	Collect VAS score for infusion site 2	
+4.0 h (± 3 min)	-5 min ^b	Collect VAS score for infusion site 3	
	0 min	Administer 15 U bolus to infusion site 3 at quick bolus speed (15 U/min)	
	+1 min ^a	Collect VAS score for infusion site 3	
	+15 min ^b	Collect VAS score for infusion site 3	
+4.5 h (± 3 min)	-5 min ^b	Collect VAS score for site 4	
	0 min	Administer 15 U bolus to infusion site 4 at quick bolus speed (15 U/min)	
	+1 min ^a	Collect VAS score for infusion site 4	
	+15 min ^b	Collect VAS score for infusion site 4	
+5.0 h (± 3 min)	-5 min ^b	Collect VAS score for site 5	
	0 min	Administer 15 U bolus to infusion site 5 at quick bolus speed (15 U/min)	
	+1 min ^a	Collect VAS score for infusion site 5	
	+15 min ^b	Collect VAS score for infusion site 5	
		Lunch	
+6.0 h (± 3 min)	-5 min ^b	Collect VAS score for infusion site 1	
	0 min	Administer 15 U bolus to infusion site 1 at quick bolus speed (15 U/min)	
	+1 min ^a	Collect VAS score for infusion site 1	
	+15 min ^b	Collect VAS score for infusion site 1	
+6.5 h (± 3 min)	-5 min ^b	Collect VAS score for site 2	
	0 min	Administer 15 U bolus to infusion site 2 at quick bolus speed (15 U/min)	
	+1 min ^a	Collect VAS score for infusion site 2	
	+15 min ^b	Collect VAS score for infusion site 2	
+7.0 h (± 3 min)	-5 min ^b	Collect VAS score for infusion site 3	
	0 min	Administer 15 U bolus to infusion site 3 at quick bolus speed (15 U/min)	
	+1 min ^a	Collect VAS score for infusion site 3	
	+15 min ^b	Collect VAS score for infusion site 3	
+7.5 h (± 3 min)	-5 min ^b	Collect VAS score for infusion site 4	

Approx. hour	Nominal timing	Activity	Other
	0 min	Administer 15 U bolus to infusion site 4 at quick bolus speed (15 U/min)	
	+1 min ^a	Collect VAS score for infusion site 4	
	+15 min ^b	Collect VAS score for infusion site 4	
+8.0 h (± 3 min)	-5 min ^b	Collect VAS score for infusion site 5	
	0 min	Administer 15 U bolus to infusion site 5 at quick bolus speed (15 U/min)	
	+1 min ^a	Collect VAS score for infusion site 5	
	+15 min ^b	Collect VAS score for infusion site 5	
		Dinner	
+9.0 h (± 3 min)	-5 min ^b	Collect VAS score for infusion site 1	
	0 min	Administer 15 U bolus to infusion site 1 at quick bolus speed (15 U/min)	
	+1 min ^a	Collect VAS score for infusion site 1	
	+15 min ^b	Collect VAS score for infusion site 1	
+9.5 h (± 3 min)	-5 min ^b	Collect VAS score for infusion site 2	
	0 min	Administer 15 U bolus to infusion site 2 at quick bolus speed (15 U/min)	
	+1 min ^a	Collect VAS score for infusion site 2	
	+15 min ^b	Collect VAS score for infusion site 2	
+10.0 h (± 3 min)	-5 min ^b	Collect VAS score for site 3	
	0 min	Administer 15 U bolus to infusion site 3 at quick bolus speed (15 U/min)	
	+1 min ^a	Collect VAS score for infusion site 3	
	+15 min ^b	Collect VAS score for infusion site 3	
+10.5 h (± 3 min)	-5 min ^b	Collect VAS score for infusion site 4	
	0 min	Administer 15 U bolus to infusion site 4 at quick bolus speed (15 U/min)	
	+1 min ^a	Collect VAS score for infusion site 4	
	+15 min ^b	Collect VAS score for infusion site 4	
+11.0 h (± 3 min)	-5 min ^b	Collect VAS score for infusion site 5	
	0 min	Administer 15 U bolus to infusion site 5 at quick bolus speed (15 U/min)	
	+1 min ^a	Collect VAS score for infusion site 5	
	+15 min ^b	Collect VAS score for infusion site 5	

Approx. hour	Nominal timing	Activity	Other
+11.5 h (± 3 min)		Remove infusion sets, evaluate local infusion sites Collect image of each local infusion site after removal of the corresponding infusion set using CCI Platform	Each local infusion site should be labeled and have a unique identifier for CCI Platform image acquisition that is the same as prior to infusion
+12.5 h (± 30 min)		Participant discharge from CRU	Following the final evaluation, the participants will have the option to spend the night or be discharged from the CRU

[figure not shown]
Abbreviations: AE = adverse event; Approx. = approximately; CRU = clinical research unit; SARS-CoV-2 = severe acute respiratory syndrome coronavirus 2; VAS = visual analog scale.

- a The VAS time point of 1- minute (+1 min) is to be collected from the start of bolus infusion.
- b The VAS time points of -5 (± 2 min), and 15 (± 2 min) minutes are to be collected from start of bolus infusion.

CCI

CCI

CCI

2. Introduction

LY900014 (Lyumjev®) is an ultra-rapid-acting formulation of insulin lispro for subcutaneous (SC) and intravenous use that employs excipients, citrate and treprostinil, to accelerate time action, along with magnesium to enhance insulin stability, resulting in improved glycemic control in participants with type 1 diabetes mellitus (T1D) or type 2 diabetes mellitus.

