4.1. Overall Design

Study I8B-MC-ITTC is a 1-/2-center, participant-(Part A CCI [REDACTED]) and investigator- CCI [REDACTED] blind, 2-part randomized crossover study in adults (18 to 69 years of age, inclusive) with T1D on CSII. Approximately 46 participants will be randomly assigned to study intervention such that approximately 40 evaluable participants complete Part A CCI [REDACTED] of the study. CCI [REDACTED]
[REDACTED]
[REDACTED]

Part A of this study will be a 1-/2-center, randomized, 1 day 5-period crossover based on the order of infusion sites and depths, blinded (between infusion depths), open-label single-treatment study conducted in adults with T1D.

CCI [REDACTED]
[REDACTED]

For CCI Part A CCI, the participant will continue using his or her personal insulin pump system at the currently employed infusion site and will be responsible for performing the required actions to maintain its functionality. Participants will be instructed to avoid the use of the central abdominal area for their personal infusion sets during the CCI [REDACTED] and prior to arrival at the clinical research unit (CRU).

For Part A

1. Following an informed consent and a screening visit, participants will come to the CRU in the evening (after dinner) of Day -1 for Part A.
2. Prior to the insertion of the first infusion set, the thickness of the SC adipose tissue layer at the abdomen, arm, thigh, and buttock areas will be assessed by ultrasound and recorded in the electronic case report form (eCRF). The evaluated site should be identified with a unique identifier.
3. The infusion sites will be assessed, and an image of each local infusion site will be collected using the CCI [REDACTED] Platform (Section 8.2.5.3.1) prior to insertion of the corresponding infusion set.
4. Each Medtronic™ MiniMed™ 770G pump reservoir will be filled by a qualified site staff member with 3 mL of study treatment (sodium citrate and treprostinil in Humalog diluent with magnesium chloride [without insulin]). The pump and infusion set will be set up as described in Section 6.1.1.
5. Five pumps will be used for each participant to assess infusions into the abdominal, arm, thigh, and buttocks areas. Participants will be randomly assigned to 1 of 5 infusion site sequences as shown in Table 4 to indicate the order of the infusion sites being evaluated.

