6. Six mm cannula will be inserted into each of the designated areas (abdomen [at least 5 cm away from the umbilicus in the left or right lower quadrants], posterior aspect of the upper arm,

anterior or lateral thigh, and upper buttock), avoiding areas of lipohypertrophy or surgical scars. At the abdominal area only, a 9 mm cannula will also be inserted into the opposite side of the lower abdomen.

7. The first infusion site will be initiated, and a basal infusion rate of 1 U/h will be started. The same procedure will occur at the subsequent infusion sites according to the randomly assigned sequence with an approximately 30-minute interval between initiation of the previous infusion site. In case of immediate infusion set intolerance, a new infusion set can be inserted within the first 10 minutes of initiation of the infusion site.

Table 4 Infusion Site Sequences for Part A

	Infusion 1	Infusion 2	Infusion 3	Infusion 4	Infusion 5
Sequence 1	Arm	Thigh	Abdomen 6 mm	Abdomen 9 mm	Buttock
Sequence 2	Abdomen 6 mm	Abdomen 9 mm	Thigh	Buttock	Arm
Sequence 3	Abdomen 9 mm	Arm	Buttock	Abdomen 6 mm	Thigh
Sequence 4	Thigh	Buttock	Abdomen 9 mm	Arm	Abdomen 6 mm
Sequence 5	Buttock	Abdomen 6 mm	Arm	Thigh	Abdomen 9 mm

Note: This is an example table based on a 5x5 Latin square design; participants will be assigned an infusion sequence according to the actual schedule provided to the site.

8. Approximately 3 hours after the start of the basal infusion at 1 U/hr, a bolus dose of 15 U will be delivered at quick bolus speed (15 U/min) to each infusion site according to the treatment sequence with an approximately 30-minute interval between infusion sites.

9. A second bolus of 15 U given at quick speed (15 U/min) will be delivered approximately 6 hours after the start of the basal infusion to each infusion site according to the treatment sequence with an approximately 30-minute interval between infusion sites.

10. A third bolus dose of 15 U given at quick speed (15 U/min) will be delivered approximately 9 hours after the start of the basal infusion to each infusion site according to the treatment sequence with an approximately 30-minute interval between infusion sites.

11. Participants will rate the pain at each infusion site after each bolus dose at the following approximate time points: 5 minutes before the administration of a bolus dose and 1 and 15 minutes after the start of each bolus dose.

12. Study infusion sets with cannula and pumps will be removed.

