5.1. Inclusion Criteria

Participants are eligible to be included in the study only if all of the following criteria apply:

Informed Consent

1. Capable of giving signed informed consent as described in Section 10.1 Appendix 1, which includes compliance with the requirements and restrictions listed in the informed consent form (ICF) and in this protocol.

Age and Sex

2. Participant must be between 18 and 69 years of age, inclusive, at the time of signing the informed consent.
3. Male or Female
 - Male: no contraception required.
 - Female: contraceptive use should be consistent with local regulations regarding the methods of contraception for those participating in clinical studies. Contraception requirements for participants are provided in Section 10.4.

Type of Participant and Disease Characteristics

4. Have been clinically diagnosed with T1D for at least 1 year before screening and have continuously been using intensive insulin therapy for at least 1 year.
5. Have been using an insulin pump for at least 6 months.
6. Have an HbA1c value $\leq 9.0\%$ at screening.
7. Have a BMI of 18.5 to 35.0 kg/m², inclusive.
8. Have clinical laboratory test results within normal reference range with acceptable deviations that are judged to be not clinically significant by the investigator.
9. Have venous access sufficient to allow for blood sampling.
10. Are reliable and willing to make themselves available for the duration of the study and are willing to follow study procedures.

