8.2.5.3. Local Infusion Site Reactions

Symptoms or signs of local infusion site reactions may include erythema, induration, pain, pruritus, and edema.

Pre-specified local infusion site reaction assessments will be performed and collected at the time points indicated in the SoA (Section 1.3).

In addition, if a spontaneous ISR is reported by a participant or site staff at a non-prespecified time point, the local infusion site reaction eCRF will be used to capture additional information about this reaction (e.g., infusion site pain, erythema, induration, pruritis, and edema).

Local infusion site reactions, whether recorded as a result of the prespecified (or solicited) assessment or spontaneously reported reactions, will be recorded as AEs as clinically indicated.

Investigational site staff will be provided with separate instructions/training on how to evaluate local infusion site reactions and their severity in a consistent manner.

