9.3.3 Exploratory Endpoint

Local ISR data (erythema, induration, categorical pain, pruritus, and edema) will be listed and summarized by infusion site location (Part A) CCI in frequency tables. Data from the exploratory CCI Platform will not be included in the CSR but may be presented in a separate report.

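### The schedule grades local reactions only after set removal, with no recorded pre-insertion grade and no new-or-worsened rule, so signs already present can enter the exploratory reaction tables

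*Protocol*

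**What the plan says.** **Timing of the reaction assessment.** In Protocol 1.3, Table 1, the comment on the local reaction row reads "After removal of each infusion set". Table 2 places the Part A assessment at +11.5 h: "Remove infusion sets, evaluate local infusion sites". Protocol 8.2.5.3 adds no other scheduled time: "Pre-specified local infusion site reaction assessments will be performed and collected at the time points indicated in the SoA". Reactions reported spontaneously at other times go on the local reaction eCRF as well.

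**Before insertion.** Protocol 4.1, Part A step 3, repeated in SAP 5.1 step 3, says "The infusion sites will be assessed, and an image of each local infusion site will be collected using the" imaging platform before the set goes in. Table 1 requires an image at both times. The pre-insertion row of Table 2 lists ultrasound and an image, and no reaction grading.

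**Choice of skin.** Cannulas are placed "avoiding areas of lipohypertrophy or surgical scars" (Protocol 4.1, step 6). Inclusion criterion 5 reads: "Have been using an insulin pump for at least 6 months". Participants are told to keep their own sets away from the central abdomen for at least 3 days before arrival.

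**Analysis.** The exploratory endpoint concerns the incidence and severity of local reactions. SAP 9.3.3 states: "Local ISR data (erythema, induration, categorical pain, pruritus, and edema) will be listed and summarized by infusion site location (Part A" (partly redacted from there), in frequency tables. Of the imaging data, the same section says "Platform will not be included in the CSR", but allows a separate report.

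**The concern.** Incidence means new occurrence, so it needs a before-state. Here the before-state is looked at and photographed, but no graded record of it is specified. The analysis has no step that would use one.

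The population makes the gap relevant. Everyone has worn an insulin pump for at least half a year, and Protocol 2.3 lists swelling, redness and bruising at the insertion site among the risks of pump use. The stated rules for choosing a site do not exclude skin that is already red, indurated or swollen.

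At stake is how the by-location reaction tables can be read. Signs equally common everywhere beforehand would raise every location's figure and compress true differences. Signs more common in some areas could create a difference between locations that no infusion caused.

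**Working it through.** **1. Is there a stated figure to reproduce?** Not on this point: the documents give neither an expected reaction rate nor a prevalence of signs before insertion. The only planning figure is the power for the VAS score (Protocol 9.5, SAP 7), which does not involve reaction data. It reproduces. ln(1.55) = 0.438 and SE = 0.95/√40 = 0.150. With a two-sided alpha of 0.05 and 39 degrees of freedom, the noncentral t gives 81.2%, against approximately 80% stated.

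**2. The texts side by side.**

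| Element | Before insertion | After removal |
|---|---|---|
| Site looked at | Yes (Protocol 4.1 step 3, SAP 5.1 step 3) | Yes (Tables 1 and 2, 4.1 step 13) |
| Image | Yes, every site | Yes, every site |
| Scheduled reaction assessment | None | Yes |
| Named signs tabulated in the SAP | None | Erythema, induration, categorical pain, pruritus, edema |
| New-or-worsened rule for the table | None | None |

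Step 2 of Protocol 4.1 says explicitly that fat thickness goes into the eCRF. Step 3, next to it, says no such thing about the skin assessment. New-or-worsened logic does exist, in Protocol 9.3.5 and SAP 9.3.4, but for adverse events and symptoms and not for the reaction tables.

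**3. Illustration of size (assumed rates).** Let r be the true rate of new reactions at a location and b the proportion of sites with a sign beforehand. Assume the two are independent and that a sign present beforehand is still there, and graded, at +11.5 h.

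- Expected tabulated count among n = 40: 40 × [b + (1 − b)r]
- Of these, pre-existing only: 40 × b(1 − r)

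| r | b | Tabulated | Pre-existing only |
|---|---|---|---|
| 10% | 0% | 4.0 | 0 |
| 10% | 2% | 4.7 | 0.7 |
| 10% | 5% | 5.8 | 1.8 |
| 10% | 10% | 7.6 | 3.6 |
| 5% | 10% | 5.8 | 3.8 |
| 20% | 10% | 11.2 | 3.2 |

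If only some of the earlier signs persist and are graded, b shrinks in proportion.

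**4. Effect on a comparison of two locations.**

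- Same r, different b: the spurious difference is (b₁ − b₂)(1 − r). With r = 10% and b = 10% against 2%, it is 0.08 × 0.90 = 7.2 percentage points. Against 0%, it is 0.10 × 0.90 = 9.0 points.
- Different r, same b: the true difference is multiplied by (1 − b). With true rates of 20% and 10% and b = 10%, the table would show 28% and 19%, a gap of 9 points instead of 10. The ratio falls from 2.0 to 28/19 = 1.5.

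The bias can therefore go either way, and the documents do not say which case applies.

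**The case against.** The case for leaving the plan alone has substance.

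- **A baseline of sorts exists.** Each site is assessed and imaged before insertion, under an identifier that is the same at both times, and the exploratory objective names that imaging platform as its instrument. This stands, and it would be wrong to say the study has no pre-insertion information. But the platform data stay out of the CSR tables. An image also cannot show pruritus or pain and is poorly suited to induration.
- **Staff may already discount old signs.** The evaluation after removal is aimed at acute reactions, and grading instructions are supplied separately and are not visible here. They may deal with signs already present. So such signs can be counted, but a reader who infers that they will be, or that incidence is overstated, goes beyond the documents.
- **Direction.** A reader might infer that the abdomen would look worst, as a common site for personal sets. The documents do not support that. The central abdomen is the only area where prior personal use is restricted. That restriction may not reach the lower-quadrant study sites, and nothing comparable covers the arm, thigh or buttock.
- **Depth.** The 6 mm and 9 mm abdominal sites are separate rows of the same table, so the missing rule covers both. They lie on opposite sides of the same participant's lower abdomen, and nothing in the documents suggests that earlier signs would differ between them.
- **Adverse events.** A reader might conclude that treatment-emergence under SAP 9.3.4 cannot be decided without a grade. It can. Adverse events are collected from consent and reviewed on Day -1, and the investigator has the pre-insertion assessment and image.
- **Low stakes.** The tables are exploratory and descriptive, with no test planned. This stands and limits the weight of the point.

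**Conclusion.** The point holds in a limited form. Reaction grading is scheduled only after removal, the pre-insertion assessment has no specified grade or eCRF record, and SAP 9.3.3 has no new-or-worsened rule. As planned, the by-location tables cannot separate signs already present from reactions to the infusion.

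The size and direction of any resulting bias are unknown. The figures above (up to 3.8 extra counts per 40 sites, or a spurious gap of 7 to 9 points under unequal prevalence) rest on assumed rates, on independence, and on earlier signs persisting to the end of the day. They show what the gap could do and are not an estimate of what it will do.

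The primary and secondary VAS analyses and the sample size are unaffected. The point still merits action because a grade not taken before insertion cannot be reliably recovered afterwards.

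**What to change.** **Protocol.** In Table 1, extend the comment on the local reaction row to cover both times: before insertion and after removal of each set. Add the grading to the pre-insertion row of Table 2. In Section 4.1 step 3, state that the same signs are graded and entered on the existing local reaction eCRF.

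**SAP 9.3.3.** Define a tabulated reaction as a sign that is absent before insertion and present after removal, or of higher severity after than before. Tabulate these by location, and list pre-existing signs separately. The pre-insertion grade can also support classification under SAP 9.3.4, though that does not depend on it.

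If the separate grading instructions already require a recorded pre-insertion grade, the protocol and SAP need only say so and add the tabulation rule.

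**Cost.** Five short gradings per participant (46 × 5 = 230 in all) at an assessment that is already required, one more time point on an existing eCRF page, and a short SAP addition. No extra visit or participant is needed. The downsides are a few minutes before insertion and slightly lower reported reaction counts.
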